# Clinical Protocol Synopsis

**STUDY TITLE:** A Phase II, Randomized, Double-Blind, Placebo-Controlled Study of Bermekimab in Patients with Moderate to Severe Atopic Dermatitis

**Sponsor:**

XBiotech USA, Inc.

**Sample Size:**

Approximately 90 patients will be enrolled in the US

**Approximate Duration:**

The duration of subject participation in the randomized, double-blind, placebo-controlled portion of the trial is approximately 40 weeks: including a screening period of up to 30 days, a 32-week treatment period, and 4-week follow-up period.

**Study Endpoints:**

***Primary Endpoint(s):***

- Percentage of patients achieving Eczema Area and Severity Index-75 (EASI-75) ( $\geq 75\%$  improvement from baseline) at week 16.

***Secondary Endpoints:***

- Percentage of patients achieving  $\geq 4$ -point improvement (reduction) in the weekly average peak daily Pruritus Numeric Rating Scale (NRS) score from baseline to weeks 4, 8, 12, 16, and 32 in patients with baseline score  $\geq 4$ .\*
- Percentage of patients achieving  $\geq 4$ -point improvement (reduction) in the weekly average overall Pruritus Numeric Rating (NRS) from baseline to weeks 4, 8, 12, 16, and 32 in patients with baseline score  $\geq 4$ .\*
- Percentage of patients achieving  $\geq 4$ -point improvement (reduction) in the weekly average peak daily Pain Numeric Rating Scale (NRS) score from baseline to weeks 4, 8, 12, 16, and 32 in patients with baseline score  $\geq 4$ .\*

- Percentage of patients achieving  $\geq 4$ -point improvement (reduction) in the weekly average overall Pain Numeric Rating (NRS) from baseline to weeks 4, 8, 12, 16, and 32 in patients with baseline score  $\geq 4$ .\*
- Percentage of patients achieving EASI-75 ( $\geq 75\%$  improvement in Eczema Area and Severity Index Score [EASI] from baseline) at weeks 4, 8, 12, and 32.\*
- Percentage of patients achieving an Investigators Global Assessment (IGA) score of 0 or 1 (on a 5-point scale) and a reduction in this measure from baseline of at least 2 points at week 16.
- Percentage of patients achieving EASI-90 ( $\geq 90\%$  improvement in Eczema Area and Severity Index Score [EASI] from baseline) at weeks 12, 16, and 32.\*
- Change in Dermatology Life Quality Index (DLQI) from baseline to weeks 8, 12, 16, and 32.\*
- Change in Hospital Anxiety Depression Scale (HADS) (Anxiety) from baseline to weeks 8, 12, 16, and 32.\*
- Change in Hospital Anxiety Depression Scale (HADS) (Depression) from baseline to weeks 8, 12, 16, and 32.\*
- Change in Patient Oriented Eczema Measure (POEM) Scores from baseline to weeks 8, 12, 16, and 32.\*
- Change in SCORing Atopic Dermatitis (SCORAD) score from baseline to weeks 8, 12, 16, and 32.\*
- Change in Global Individual Signs Score (GISS) from baseline to weeks 8, 12, 16, and 32.\*

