### **10.2 RANDOMIZATION**

A centralized block randomization schedule with a 1:1:1 allocation ratio will be utilized using an electronic randomization system. Patients will be randomly assigned to either the bermekimab weekly injection group (arm 1), the bermekimab every other week injection group (arm 2), or the placebo group (arm 3). The randomization schedule will be stratified by baseline EASI severity (less severe (EASI  $\geq 16$  and  $< 28$ ) or more severe (EASI  $\geq 28$ )).

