#### **10.5.3.2 Secondary Efficacy Analyses**

Secondary and exploratory efficacy endpoints will be summarized using descriptive statistics for continuous variables (n, mean, standard deviation, median, minimum and maximum value) and number and percentage for categorical variables.. The 95% CI of the mean change from baseline will be provided. The change from baseline in these endpoints at each week will be analyzed using a restricted maximum likelihood (REML)-based mixed model for repeated measures (MMRM) with fixed effects for treatment, week, stratification factor (baseline EASI severity), baseline score, baseline score by week interaction, and the treatment-by-week interaction, if applicable. The impact of the stratification factor will also be assessed. Categorical variables will be analyzed using CMH tests as used for the primary efficacy analysis. Full details will be provided in the SAP.

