## 5. EFFICACY

### 5.1. General Method of Analysis

Unless specified otherwise, efficacy data summaries will be provided by treatment group for the FAS. Statistical comparisons will be made between each of the bermekimab treatment groups (qw, q2w) and the placebo treatment group.

In general, for response efficacy endpoints, treatment comparisons will be performed using a Cochran-Mantel-Haenszel (CMH) test stratified by the baseline EASI severity (less severe  $EASI < 28$ , more severe  $EASI \geq 28$ ) or the Fisher's Exact test in case of rare events. For continuous efficacy endpoints, treatment comparisons will be performed using a Mixed-Effect Model Repeated Measure (MMRM) with treatment group, visit, baseline EASI severity (less severe, more severe) and baseline value for the efficacy endpoint as explanatory factors. The MMRM model will also include treatment group by visit interaction, baseline EASI severity by visit and baseline

value by visit interaction as additional explanatory factors. In addition, treatment differences and their associated 95% confidence intervals will be presented.

Descriptive statistics, such as mean, median, standard deviation, minimum and maximum, interquartile range for continuous variables, and counts and percentages for categorical variables will be used to summarize the data. Graphical data displays and subject listings may also be used to summarize the data.

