## **5.4. Secondary Efficacy Endpoints**

This section outlines the definition and analyses of these secondary endpoints related to NRS, EASI, IGA, DLQI, HADS, POEM, SCORAD, and GISS. Data from all participants in FAS will be included and analyzed according to the randomized treatment groups. For participants randomized to placebo, only participants who crossed over to receive bermekimab at Week 16 will be included in the efficacy summaries for the visits after Week 16. All statistical testing will be performed at the 2-sided 0.05 significance level. Nominal p-values will be presented.

Secondary efficacy endpoints will be summarized using descriptive statistics for continuous variables (n, mean, standard deviation, median, minimum and maximum value) and number and percentage for categorical variables. Continuous endpoints will be analyzed using a MMRM model to test the difference between treatment groups and adjust for missing data. The MMRM will include treatment, visit, baseline EASI severity, baseline score, baseline score by visit interaction, baseline EASI severity by visit interaction and the treatment-by-visit interaction, if applicable. The Least Square mean (LSmean) estimates and their corresponding 95% confidence interval (CI) will be provided at each time points. In addition, the estimates of LSmean difference and 95% CIs between treatment groups will be provided over time through Week 16 and p-values will be calculated at Week 16.

For the MMRM model, an unstructured covariance matrix for repeated measure within a participant will be used. In case that convergence cannot be achieved, autoregressive (1) covariance structure will be used.

For binary response endpoints, treatment comparisons will be performed using a Cochran-Mantel-Haenszel (CMH) test stratified by baseline EASI severity with missing data imputed with Non-Responder Imputation (NRI) defined in Section 5.2.2. In case of rare events, the Fisher's Exact test will be used for treatment comparisons in binary response endpoints.

Graphical data displays may also be used to summarize the over time data if applicable.

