#### **5.4.3.2. Analyses Related to NRS**

- The improvement (reduction) from baseline in NRS score (weekly average overall pain, weekly average worst daily pain, weekly average overall Itch, weekly average worst daily Itch) at Week 16 will be compared between each bermekimab group and placebo group using a MMRM model.
- The proportion of participants who achieve  $\geq 4$ -point improvement (reduction) in NRS score (weekly average overall pain, weekly average worst daily pain, weekly average overall Itch, weekly average worst daily Itch) from baseline at Week 16 will be compared between each bermekimab group and placebo group using a CMH test stratified by baseline EASI severity in patients with baseline score  $\geq 4$ .
- The improvement (reduction) from baseline in NRS score (weekly average overall pain, weekly average worst daily pain, weekly average overall Itch, weekly average worst daily Itch) will be summarized by treatment group over time.
- The proportion of participants who achieve  $\geq 4$ -point improvement (reduction) in NRS score (weekly average overall pain, weekly average worst daily pain, weekly average overall Itch, weekly average worst daily Itch) from baseline will be summarized by treatment group over time in patients with baseline score  $\geq 4$ .

In addition, two supplementary analyses (a) improvement from baseline in NRS itch score at Week 16, and (b) improvement from baseline in NRS itch score over time will be performed with the following data handling rules:

- Data is considered as missing after the discontinuation of study intervention, missing data is handled through the MMRM model.

- Data will be analyzed based on observed data regardless of whether the subject discontinued treatment or have missing data.

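### The Week 16 itch and pain responder tests require a fixed 4-point drop but do not adjust for baseline NRS, so a chance imbalance can shift the estimate and a little power is lost

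*Protocol*

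**What the plan says.** The protocol lists four NRS responder endpoints (peak and overall, for pruritus and for pain). Each needs a reduction of at least 4 points in a weekly average and is restricted to patients with a baseline of at least 4. The first reads "improvement (reduction) in the weekly average peak daily Pruritus Numeric Rating Scale (NRS) score from baseline to weeks 4, 8, 12, 16, and 32".

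On the test, protocol 10.5.3.2 says "Categorical variables will be analyzed using CMH tests as used for the primary efficacy analysis", that is, CMH stratified by baseline EASI severity. SAP 5.4.3.2 narrows this to one visit. The responder proportion "from baseline at Week 16 will be compared between each bermekimab group and placebo group using a CMH test stratified by baseline EASI severity", and the proportions over time are summarised by group. SAP 5.1 and 5.4 substitute Fisher's exact test when events are rare. Secondary p-values are nominal.

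On balance, protocol 10.2 says "The randomization schedule will be stratified by baseline EASI severity". NRS is not a stratifier.

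The same four scores are also analysed as continuous change: the improvement "at Week 16 will be compared between each bermekimab group and placebo group using a MMRM model". That model does carry the baseline. SAP 5.1 lists the "baseline value for the efficacy endpoint as explanatory factors", and SAP 5.4 says "The MMRM will include treatment, visit, baseline EASI severity, baseline score, baseline score by visit interaction".

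SAP 4.1 adds that further analyses adjusting for baseline differences may be done if imbalances are found. It names no covariate, method or trigger.

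**The concern.** A fixed 4-point drop is a harder target the closer a patient starts to 4. If response depends on baseline NRS, an arm that starts higher by chance has an easier target. A test stratified only by EASI severity cannot separate that from a drug effect. The plan accepts this reasoning for the continuous form of the scores but not for the responder form, which is the one that the protocol declares as secondary.

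The stake is how the itch and pain results are read in this one trial. SAP 2.4 places both scores in the Week 16 database lock, whose data are mainly for planning later development. The groups are small. About 90 patients in three arms is about 30 per arm, and the subset with baseline at least 4 is smaller: itch entry is at 3 or more, and pain has no entry threshold.

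**Working it through.** **The plan's own figure.** The trial is sized on EASI-75, 60% vs 20%. With pooled variance, n = [1.960·√(2·0.4·0.6) + 0.842·√(0.6·0.4 + 0.2·0.8)]² / 0.4² = (1.358 + 0.532)² / 0.16 = 22.3, so 23 per arm and 69 in total. This agrees with protocol 10.1. No figure is given for the NRS responders, and nothing below changes the 69.

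**Inputs that had to be assumed.** The documents give no NRS mean, SD or link between baseline and response. Assumed: baseline worst itch around 7.5 with SD 1.7, confined to 4–10 (SD about 1.39 after truncation); 28 patients per arm; fractional reduction R normal with SD 0.3 and mean 0.25 on placebo, 0.50 on active.

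**Step 1: response by baseline.** A patient at baseline b responds if R ≥ 4/b, so P = 1 − Φ((4/b − mean)/0.3).

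| Baseline | Active | Placebo |
|---|---|---|
| 4 | 4.8% | 0.6% |
| 6 | 28.9% | 8.2% |
| 8 | 50.0% | 20.2% |
| 10 | 63.1% | 30.9% |

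**Step 2: shift per point of imbalance.** A 1-point difference in arm means moves the responder difference by about the average of the two slopes. From 4 to 6: (12.1 + 3.8)/2 = 7.9 percentage points. From 6 to 8: (10.5 + 6.0)/2 = 8.3. From 8 to 10: (6.5 + 5.3)/2 = 5.9. Simulation under proportional-reduction models gave 5 to 10. A wider set of linear models gave about 0 (follow-up moves one-for-one with baseline) to 14 (follow-up unrelated to baseline).

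**Step 3: likely size of the imbalance.** SD of the difference in arm means = 1.39·√(2/28) = 0.37. A difference beyond 0.5 in either direction has z = 0.5/0.37 = 1.35, about 18% of trials. A difference beyond 1.0 has z = 2.70, about 0.7%. A 1-SD imbalance shifts the result by 0.37 × 5 to 0.37 × 10, about 2 to 4 percentage points. For scale, the standard error of the difference at illustrative rates of 20% vs 50% is √(0.16/28 + 0.25/28) = 0.121, about 12 points.

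**Step 4: type I error.** Over all randomisations the planned CMH held its size: 4.6–5.1% two-sided in one set of simulations, 4.8–5.1% in another. In the roughly 9% of trials where the imbalance exceeds 0.5 in favour of bermekimab, its one-sided false-positive rate was 4.5–7.3% against a nominal 2.5%. With covariance adjustment it was 1.8–3.0%. Overall size of the adjusted test was 4.1–5.4% at 14–28 per arm.

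**Step 5: power.** Covariance adjustment raised power from 55.8 to 57.7%, 78.4 to 83.3% and 87.4 to 91.4% in three settings. In separate runs it rose from 56.8 to 59.0% (28 per arm) and 47.4 to 49.2% (22 per arm). As a rough check, baseline NRS explained 7–11% of response variance within strata, which is worth 1/0.93 = 1.08 to 1/0.89 = 1.12 times the patients. At 80% power, Φ(2.802·√1.075 − 1.960) = 83% and Φ(2.802·√1.124 − 1.960) = 84%.

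Two alternatives did less well. Adding a split of NRS at 7 to the CMH strata changed power by −2 to +3 points. A logistic likelihood-ratio test gained 0 to 4 points in most settings and 7 to 8 in the most extreme, but its type I error was 5.7–6.7%, so those gains are upper figures.

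**The case against.** The strongest reply is that nothing is invalid here. Randomisation protects the test, and higher error in trials whose imbalance favours the drug is offset where it does not. The same holds for any prognostic covariate left out of any randomised comparison. This stands. A reader might infer from the 4.5–7.3% figure that type I error is inflated. It is not: that rate applies to a selected fraction of trials.

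A reader might also count 20 of the 52 protocol secondary endpoint-by-week entries (4×5 of 4×5 + 4 + 1 + 3 + 6×4) as affected. The SAP does not support that reach. It tests the NRS responders at Week 16 only, so four entries, each for two regimens. At Week 32 there is no placebo group left.

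Nor is it right that the plan has no adjustment for baseline NRS. The MMRM on the same scores at the same visit adjusts for it, which limits the harm, and SAP 4.1 permits adjusted analyses. That provision is optional, names no method, and would be chosen after the imbalance is seen. It is therefore no substitute for a prespecified analysis.

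Finally, the size rests on an assumed model. Proportional reduction builds in dependence on baseline, and if response does not depend on baseline the gain is zero. The tests are nominal secondary ones in a phase II trial that is not sized on them.

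**Conclusion.** The point holds in a limited form. The four Week 16 NRS responder comparisons leave out the baseline value on which a fixed 4-point target probably depends, although the MMRM on the same scores includes it. The planned CMH is valid overall. What is lost is protection of the single-trial estimate against chance imbalance, plus a little power: about 5–10 percentage points of shift per 1-point imbalance, about 2–4 for a typical one, and roughly 1–5 power points, or none without dependence on baseline. The direction follows from the endpoint definition. The amounts rest on the assumed NRS distribution, the proportional-reduction model and 28 or fewer patients per arm. This is a cheap improvement and not the repair of an invalid test.

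**What to change.** In SAP 5.4.3.2, prespecify for the Week 16 NRS responders an analysis adjusted for the continuous baseline value of the same NRS score within the EASI-severity strata, using the randomisation-based covariance-adjusted CMH. Report the adjusted difference with its 95% CI beside the planned CMH. Keep Fisher's exact test where events are rare. Ordinary logistic regression and further splitting of the CMH strata are not advised, for the reasons shown under power.

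Do the same for the DLQI comparison in SAP 5.4.5.2, where a drop of 5 or more points is required from a baseline of at least 5. It has the same structure.

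Cost: SAP wording, one more program and a less familiar method. No new data are needed, and no covariate can be missing, because the analysis set is defined by that baseline value. If the adjusted analysis is made the main one, the SAP should also note the departure from protocol 10.5.3.2.

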***Exploratory Endpoints:***

- Percentage of patients achieving an IGA score 0 or 1 (on a 5-point scale) and a reduction in this measure from baseline of at least 2 points at week 12.
- Change in Eczema Area and Severity Index Score (EASI) from baseline to weeks 8, 12, 16, and 32.
- Change from baseline to week 4 in Dermatology Life Quality Index (DLQI).
- Patients (%) achieving 50% reduction in SCORAD Score at Weeks 4, 8, 12, 16, and 32.\*
- Patients (%) achieving 75% reduction in SCORAD Score at Weeks 4, 8, 12, 16, and 32.\*
- Patients (%) achieving 90% reduction in SCORAD Score at Weeks 4, 8, 12, 16, and 32.\*
- Change from baseline to week 8, 12, 16, and 32 in percent Body Surface Area (BSA).\*

***Safety Endpoints:***

- Incidence of skin infection treatment-emergent adverse events (TEAEs) requiring systemic treatment from baseline through week 16 and 32.
- Incidence of treatment-emergent serious adverse events (TESAEs) from baseline through week 16 and 32.
- Incidence of TEAEs leading to treatment discontinuation from baseline through week 16 and 32.

\*Each listed time point (in weeks) will be measured separately and treated as an individual endpoint.

## **Trial Design:**

This is a phase II, randomized, double-blind, placebo-controlled study to further establish the efficacy and safety and explore dose effects for bermekimab monotherapy in adults with moderate to severe Atopic Dermatitis (AD). Patients will be assessed for study eligibility at the initial screening visit after providing informed consent. Thirty days are allowed in the screening window to complete all screening procedures and randomize the subject. During the screening period, certain treatments will be washed out, as applicable, according to eligibility requirements. Patients who fail initially may be re-screened once based on the investigator discretion but only if inclusion criteria are met at time of re-screening.

The study is approximately 40 weeks (30 day screening period, 32-week treatment period and a 4-week follow-up period) for all subjects.

The primary efficacy endpoint is the percentage of patients achieving  $\geq 75\%$  improvement from baseline in EASI score at week 16. The EASI is a validated measure used in clinical practice and clinical trials to assess the severity and extent of AD. Secondary measures will include Pruritus NRS, Pain NRS, SCORAD, POEM, GISS, DLQI, HADS, BSA and IGA.

Patients who meet the eligibility criteria at screening will be randomized in a 1:1:1 ratio to one of two treatment arms or placebo:

- Arm 1: 800 mg of bermekimab + placebo loading dose (2mL SC injection containing 400 mg of bermekimab and one 2mL SC injection of placebo) at week 0 followed by weekly (qw) subcutaneous (SC) injections of 400 mg bermekimab through week 31
- Arm 2: 800 mg loading dose of bermekimab (2 x 400 mg SC injections) at week 0 followed by subcutaneous (SC) injections of 400 mg bermekimab every other week (q2w) alternating with matching placebo q2w through week 31.
- Arm 3: 4mL loading dose of placebo (2 x 2mL SC injections) at week 0 followed by weekly placebo injections from week 1 through week 15. Patients in Arm 3 will begin to receive weekly (qw) blinded subcutaneous (SC) injections of 400 mg bermekimab beginning at week 16 through week 31.

In order to maintain blinding, all patients will receive two injections at week 0 and 16, followed by weekly injections from week 1 to 31. Additionally, at least one qualified individual will be designated at each study site to perform all preparation and injection of the investigational product. The designated

injector(s) should have no other contact with the participant during the study, should not discuss the participant's treatment with the participant, participant's caregiver, or other site personnel at any time, and will not be permitted to review the participant's medical records, questionnaires, or the electronic CRF prior to each injection. The designated injector(s) should be documented in the source documents at each visit.

Study treatment will be administered weekly in the clinic for 31 weeks with weekly office visits for 32 weeks. Patients will remain at the study site for a minimum of 30 minutes (+/- 10 minutes) after injections at weeks 0, 1, 2, 16, 17 and 18 injections for safety monitoring.

During the 32-week treatment period, patients will attend weekly clinical study visits. Clinical assessments, collection of samples for bermekimab concentrations, and safety testing will be performed at specified clinic visits. After completion of the 36-week study period, data will be locked and analyzed for safety and efficacy endpoints for all arms. In addition to the analyses that will be performed following the formal database lock at the end of the study at Week 36, an additional database lock may be performed at Week 16, and interim analyses utilizing unblinded efficacy data available as the study progresses, may also be conducted to help plan potential future development activities. An internal interim analysis committee (IAC) will be established to review the interim data and formulate recommended decisions/actions. The IAC will consist of at least a clinician and a statistician (neither of whom are involved in study conduct or compound development), one of whom will chair the committee, and may also include other members as required by the nature of the IAs. Details will be provided in a separate IAC charter, which will define the organization and roles and responsibilities of the committee, possible recommendations or requests, and the communication process following IA reviews. Results from the Week 16 database lock and/or interim analyses will not be disseminated to investigators or subjects participating in the study. In addition, results of the interim analyses will not be disseminated to individuals associated with the conduct of the study.

Patients will be monitored at a follow up visit (visit 34/week 36) for safety and clinical assessments after completing the 32 week treatment period.

